
diarrhea following VR-AD-1005 administration.
 
 • Evaluation of safety and tolerability of VR-AD-1005 in addition to standard of care (SoC) versus SoC with placebo in adults with symptomatic cholera via documentation of adverse events, physical examination, and vital signs. 	
the treatment for both treatment groups.
 
 • Time until clinical recovery (defined as disappearance of watery stool and two consecutive passages of soft stool). Duration of diarrhea until the passage of first non-watery stool (soft/loose) or no stool for 12 hours or the end of treatment (72 hours) will be derived from date and time records in daily stool charts. • Number of subjects with clinical recovery as above within treatment group. The number of subjects with clinical recovery will be recorded as total for the entire treatment duration, and as number of recoveries per each 24-hour period of treatment. • Number of unscheduled IV rehydration episodes per treatment. The number of unscheduled IV rehydration episodes per treatment will be recorded for the entire duration of the treatment. Unscheduled IV rehydration is defined as "receipt of IV fluid during the maintenance phase of hydration due to development of severe dehydration or some dehydration with high purging (>15 ml/kg/hour) or persistent vomiting (>3 episodes/hour), or failure to take ORS for any reason" • Duration of IV rehydration for the entire treatment period per treatment group and per each 24- hour period of treatment. • Safety will be measured by the proportion of patients that will present with AE/SAE as defined in Appendix II following administration of VR-AD- 1005. 	
measure of hydration status of the participants, as well as providing a measure of the duration of the illness. Dehydration is the primary cause of death in cholera; duration of illness is the primary measure of the burden on the healthcare system and quality of life/productivity loss for cholera patients. Assessment of reduction in the need for unscheduled intravenous rehydration and time until switch to oral rehydration therapy will allow to assess the benefit of VR-AD-1005 for in-patient management of cholera cases. Thus, secondary end-points allow to characterize the benefits related to potential improvements in the clinical course of the disease, case management and quality of life for cholera patients.

---	--	--

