6.0 Data Analysis

Describe plans for data analysis, including stratification by sex, gender and diversity. Indicate whether data will be analysed by the investigators themselves or by other professionals. Specify what statistical software packages will be used and if the study is blinded, when the code will be opened. For clinical trials, indicate if interim data analysis will be required to determine further course of the study.

Data analysis must comply with ICH E9 Guideline and ICH E9(R1) Guideline. All relevant data collected in the trial should be considered in the statistical considerations section.

The analysis will be conducted on all participant data at the time the trial ends.

Statistics for primary end-point data and parametric secondary end-point data will be presented via means (alternatively, LSMEANS) with standard deviations; primarily two-tailed Student's t-test will be used for analysis with significance level of $p \leq 0.05$. For non-parametric analysis, such as lifetime data, Kaplan-Meier analysis will be used with significance level of $p \leq 0.05$. Some data might be expressed and analyzed as % values, such as the occurrence of unscheduled IV rehydration.

Analysis of secondary endpoints will be performed through the same method of the primary endpoint, which is found via a one- sided two sample unequal variance Student's t-test. The scale for each secondary endpoint will be nominal and will be determined at a single endpoint, which is at the end of intervention. The results will be presented by LSMEANS (Least-squares Means) with standard errors.

Primary Endpoint:

Reduction in stool output volume (ml/hour) over a treatment period measured and plotted as total stool output during 12-hour stool collection at every 12 hours for 72 hours.

Secondary Endpoints:

- Time until the stool volume output of 200mL/hour or less. Duration of stool output in excess of 200mL/hour per patient will be recorded between the start and end of the treatment for both treatment groups.
- Time until recovery. Duration of diarrhea until the passage of first non-watery stool or no stool for 12 hours or the end of treatment (72 hours) will be derived from date and time records in daily stool charts.

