Number of unscheduled IV rehydration episodes per treatment. The number of unscheduled IV rehydration episodes per treatment will be recorded for the entire duration of the treatment. Unscheduled IV rehydration is defined as "receipt of IV fluid during the maintenance phase of hydration due to development of severe dehydration or some dehydration with high purging (>15 ml/kg/hour) or persistent vomiting (>3 episodes/hour), or failure to take ORS for any reason"
- Duration of IV rehydration for the entire treatment period per treatment group and per each 24-hour period of treatment.
- Number of recovered subjects within treatment group. The number of recovered subjects will be recorded as total for the entire treatment duration, and as number of recoveries per each 24-hour period of treatment.
- Safety will be measured by the proportion of patients that will present with AE following administration of VR-AD-1005.

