Secondary Endpoint 1, assessment of hydration control. There are two measurable parameters to be assessed in the patient hydration. Parameter 1 is the number of unscheduled hydration episodes. The numbers will be derived from the individual rehydration records, and the number of patients receiving IV rehydration will be expressed in % and compared for control and study intervention group. Alternatively, total number of IV rehydration episodes can be expressed as means for control and study intervention group and analyzed using Student's t-test. Parameter 2 is the volume of the oral rehydration solution received during the course of interventional treatment. Total volume of rehydration solution (oral and IV where applicable) will be derived from the individual rehydration records, expressed in ml/kg of patient weight, and analyzed as means using unpaired Student's t-test. Analysis subgroups will include 1) total hydration received over the course of study after first administration of interventional medication, and 2) hydration received during first 12 hours and 3) hydration received during first 24 hours.

Secondary Endpoint 2. Assessment of duration of diarrhea. Total duration of diarrheal illness is an important parameter in the assessment of antidiarrheal treatment efficacy. Study intervention is expected to reduce the overall duration of the diarrhea. Duration of diarrhea is assessed from first administration of study intervention until the termination of diarrhea, which is defined as first formed stool, or no stool for 12 consecutive hours. Duration of diarrhea will be derived from individual stool charts. Kaplan-Meier survival curves will be built to compare duration of diarrhea between control and intervention groups.

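### End of treatment at 72 h is listed among the events that stop the time-to-recovery clock, and no censoring rule is given, so a patient still purging at 72 h can receive a completed recovery time and be counted as recovered

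*Combined protocol and SAP*

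**What the plan says.** Four places bear on when diarrhoea ends and who has recovered.

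- **Section 5.0, Table 1, secondary endpoints.** The bullet opens with a clinical definition: "Time until clinical recovery (defined as disappearance of watery stool and two consecutive passages of soft stool". The next sentence derives the duration differently, to the "first non-watery stool (soft/loose) or no stool for 12 hours or the end of treatment (72 hours". The following bullet counts "Number of subjects with clinical recovery as above within treatment group". The primary objective in the same table uses the two-soft-stool definition too, and names end of study treatment as a separate alternative to recovery.
- **Section 6.0, secondary endpoints.** The clinical definition is gone and only the three-way rule remains: "Duration of diarrhea until the passage of first non-watery stool or no stool for 12 hours or the end of treatment (72 hours". The count is "Number of recovered subjects within treatment group", with no definition of recovered.
- **Section 6.3, Secondary Endpoint 2.** Duration runs "until the termination of diarrhea, which is defined as first formed stool, or no stool for 12 consecutive hours". End of treatment is absent. The method is that "Kaplan-Meier survival curves will be built to compare duration of diarrhea between control and intervention groups", with no censoring rule and no named test.
- **Section 6.0, methods.** Lifetime data go to Kaplan-Meier, but another paragraph sends the secondary endpoints to a one-sided unequal-variance t-test, which cannot censor.

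**The concern.** Reaching 72 h is the end of the observation window. A first non-watery stool and 12 stool-free hours are outcomes. Joining all three with 'or' under the label of time until recovery removes the distinction between a patient who recovered at 72 h and one who was still purging then.

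Three results are exposed: the number recovered (overall and in the last 24-hour period), the Kaplan-Meier curve at its right-hand end, and any t-test that takes 72 h as an observed duration. Patients unresolved at 72 h are the ones in whom an antisecretory drug had most room to help. Counting them as recovered can therefore hide a true difference as easily as it flatters an arm.

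A related gap is that treatment can stop before 72 h (section 4.11), and stool is collected for efficacy only while treatment lasts (section 4.5.2). The plan does not say what duration or recovery status such a patient receives.

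**Working it through.** **1. Plan's own figure.** The plan gives no power or precision for time to recovery. Its only power figures concern stool output: a difference of 0.33 × 280 = 92.4 g/kg, SD 156, two-sided 5%. The noncentrality is 92.4/(156·√(2/n)), which is 2.96 at 50 per arm and 3.63 at 75. Exact t-test power is 0.835 and 0.950, against the stated 0.82 and 0.94. These agree within two points and are not affected by this issue.

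**2. The rules applied to three illustrative patients**

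| Patient | Table 1 clinical definition | Duration rule in Table 1 and 6.0 | Section 6.3 |
|---|---|---|---|
| Soft stools from 33 h, none formed, no 12 h gap | recovered once the second soft stool has passed | 33 h | not ended |
| Watery throughout to 72 h | not recovered | 72 h, complete | not ended; no censoring rule |
| Treatment stopped at 20 h, still purging | not recovered | not covered (the text fixes 72 h) | not covered |

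The second row is the point at issue. The first shows that the criteria also differ on what counts as an ending.

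**3. Share unresolved at 72 h.** Section 6.3 gives a mean of 30-35 h. The shape is an assumption.

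- Lognormal with mean m and log-SD s: P(T > 72) = 1 − Φ{[ln 72 − (ln m − s²/2)]/s}. For m = 30, s = 0.4, z = (4.277 − 3.321)/0.4 = 2.39 and P = 0.8%. For m = 35, s = 0.6, z = (4.277 − 3.375)/0.6 = 1.50 and P = 6.7%. These shapes put 81-93% of patients past recovery by 50 h, consistent with section 6.2.1, which expects a majority within 30-50 h.
- Exponential: exp(−72/30) = 9.1% and exp(−72/35) = 12.8%.
- Out of 75 placebo patients, that is about 1 to 5 (lognormal) or 7 to 10 (exponential).

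**4. Effect on the recovered count.** The plan sets no effect size for duration, so assume a 33% shortening.

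- Exponential, means 32.5 h and 0.67 × 32.5 = 21.8 h: true recovered shares are 1 − exp(−72/32.5) = 89% and 1 − exp(−72/21.8) = 96%.
- Lognormal, mean 33 h, log-SD 0.5: 96.5% and 99.5%.

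Under the literal section 6.0 rule, with everyone followed to 72 h, both become 100% versus 100%.

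**5. Effect on the tests.** If all n patients still at risk at 72 h are coded as events, then d = n and d₁ = n₁. The log-rank contribution d₁ − d·n₁/n is 0, and the variance term, which carries the factor (n − d), is also 0. The statistic is unchanged; in simulation the largest difference in Z was 0.0. The Kaplan-Meier estimate does change: it drops to zero at 72 h. A t-test compares means cut off at 72 h. In the exponential example these are 32.5 × 0.891 = 29.0 h and 21.8 × 0.963 = 21.0 h, a difference of 8.0 h against 10.7 h uncut.

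**6. Stops before 72 h, as a sensitivity check only.** Assumptions: no drug effect, 75 per arm, lognormal mean 33 h, log-SD 0.5, stops uniform over 0-36 h, two-sided 5% log-rank, 2,000 runs.

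| Assumed stops, placebo vs active | Rejection if censored | Rejection if coded as endings | Truly recovered |
|---|---|---|---|
| 5% vs 20% | 5.0% | 13.2% (12.9% favouring active) | 92.9% vs 81.9% |
| 5% vs 10% | 4.8% | 5.4% (4.5% favouring active) | 92.9% vs 89.2% |
| 10% vs 10% | 5.7% | 5.0% | about 89% in both |

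The Monte Carlo standard error is about 0.5 points. With exponential durations (mean 32.5 h) and stops spread over 0-72 h, 5% vs 20% moves the rate only from 4.3% to 6.0%, so the size depends on shape and timing.

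**The case against.** The case for leaving the text alone is a fair one. Table 1 defines clinical recovery as two soft stools in a row, and the natural antecedent of its count is that defined term. The primary objective keeps recovery and end of treatment apart. Section 6.3, the most detailed analysis text, omits end of treatment and uses Kaplan-Meier, which accommodates censoring. The 72 h limb can then be read as the end of observation, and a mean restricted to 72 h is a legitimate summary.

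Much of this stands, and it rules out three stronger readings that a reader might infer:

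- **That treatment failures are scored as recoveries, so both arms reach 100% by construction.** This follows only from sections 6.0's duration rule and undefined count taken literally. A purging patient does not meet the Table 1 definition.
- **That a patient stopped early receives a short recovery time.** The text fixes end of treatment at 72 hours. Early stops are simply not addressed, apart from the general missing-data provisions of section 6.2.2.
- **That the 72 h rule inflates the error of the survival comparison.** It leaves the log-rank test unchanged. Inflation needs early stops to be coded as endings and to differ strongly between arms, and the documents give no such rates.

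What the objection does not remove is that section 6.0 carries no clinical definition, that its t-test route cannot censor, and that section 6.3 conflicts with the other text instead of clarifying it: it asks for a formed stool where Table 1 accepts a soft or loose one.

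**Conclusion.** The point holds as a conflict between definitions combined with a missing censoring rule, in a secondary endpoint. The plan as written allows a patient unresolved at 72 h to be given a completed duration and to be counted as recovered. It does not require this.

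The number of patients is small to moderate, and rests on the plan's mean duration and an assumed shape. The damage is confined to the recovered counts, the right-hand end of the Kaplan-Meier curve, and how any t-test on duration is interpreted. The primary analysis and the sample size are untouched. The early-stop figures show why a rule is needed; they do not predict what this trial will see. The change should be made before unblinding, because the choice of rule affects the reported recovery rate.

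**What to change.** 1. In Table 1 (section 5.0) and in section 6.0, delete end of treatment at 72 hours from the events that end diarrhoea.
2. In section 6.3, state that a patient who has not met the recovery criterion is censored in the Kaplan-Meier analysis at the last stool-chart time: 72 h, or earlier if charting stops.
3. In Table 1 and section 6.0, count a patient as recovered, overall and per 24-hour period, only if the criterion was met. Keep everyone in the analysis set in question in the denominator, and show early stops without recovery as not recovered.
4. Reconcile the criteria in Table 1 (primary objective and secondary endpoints), section 6.0 and section 6.3 so that one is used throughout. At present they are two soft stools in a row, first non-watery stool, first formed stool, and 12 stool-free hours. The choice is for the sponsor and the investigator.

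The cost is a few sentences and no new data. The reported recovered percentage may be slightly lower.

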6.1. Analysis set

Data for VR-AD-1005 intervention vs. placebo groups will be analyzed in the following comparison data sets:

A. Stool output comparison

B. Comparison of the number of unscheduled hydration episodes (both IV and oral, as defined above).

- C. Comparison of the total volume of the rehydration solutions used during the study.
- D. Duration of diarrheal illness will be compared between the groups.
- E. Duration of stool output in excess of 200ml/hour will be compared.
- F. Comparison for the number of AE/SAE.
- G. Comparisons for the base-line descriptive statistics.

6.2. Analysis Supporting Primary Objectives

6.2.1. Statistical Model, Hypothesis, and Method of Analysis

Primary Endpoint:

Reduction in stool output volume over a treatment period.

Primary Endpoint 1., Hypothesis 1. Treatment with VR-AD-1005 reduces stool output in patients with diarrhea due to *V. cholerae* infection. Null hypothesis is stated as no statistically significant difference in stool output volume as compared to placebo; alternative Hypothesis 1 is stated as statistically significant reduction in stool output volume in patients treated with VR-AD- 1005.

Two analytical approaches are proposed. Approach 1 will be based on the total quantity of stool purged by participant during the intervention administration period. Stool output will be expressed as g/kg body weight based on the stool charts, and the means will be compared between intervention and placebo groups using Student's unpaired t-test. In approach 2, stool purging is measured and plotted as total stool output in ml/kg/12 hours based on the individual stool collection charts. Weight of stool will be converted to volume using 1:1 weight/volume ratio. Diarrhea of cholera resolves rapidly, and majority of patients are expected to recover within 30-50 hours after randomization. 12-hour analysis increments allow a better insight into the onset and timing of the effect of study intervention as compared to cumulative data over the duration of the treatment. Means will be compared for each 12-hour period after first intervention administration using unpaired Student's t-test. Normal distribution is assumed for both cases. Analysis will be conducted in the ITT, MITT and PP groups. Missing data and outliers will be handled using imputation technique. Non-adherence and lost to follow-up patients will be categorized into the appropriate group and handled accordingly. No subtractions will be made from the ITT group after randomization assignment.

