4.4.6.3. Blinding and Unblinding

The blinding/randomization of the medication is determined when the individual patient study supplies are packaged by the IP manufacturer. Standard randomization methods are used, i.e. uneven block randomization. The study center is required to dispense the patient medication in chronological order to each of the patients entering the study. A sealed envelope containing the randomization code breaks will be given to the Investigator for safe keeping enabling easy access in the event of an emergency, requiring the code to be broken.

Management of Emergency Code Break:

The emergency code breaks will be placed by Hunazine Biotech in a sealed envelope and kept at the study center. The code must only be broken in the case of medical events which the investigator/physician in charge of the patient feels cannot be adequately treated without knowing the identity of the study medication.

Sponsor should be contacted before breaking the code. If it is not possible, and the situation is an emergency, the investigator may break the code and contact the Sponsor as soon as possible. The following information needs to be recorded in the event of an Emergency Code Break:

- Date of Code Break
- Identification of person(s) requesting the Code Break
- Reason for breaking the code
- Investigator Signature.

The person who broke the code must sign and date the envelope which, if opened at study site, will be returned to Safety Board (SB) by the SB site monitor. The patient will be withdrawn from the study.

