4.5.2. Efficacy Assessments and Procedures

- Medications review.
- Physical examination: Body weight, thirst, HEENT (note and record signs of dehydration, such as sunken eyes), skin (note and record signs of dehydration, such loss of turgor), level of consciousness, vomiting.
- Hydration status should be assessed in each participant including assessment of IV fluids, oral ORS intake and oral water intake. The volume of rehydration solutions received by the participant is recorded continuously for both enteral and parenteral rehydration for the entire duration of the treatment. Access to unaccounted water (i.e. tap water) should be restricted, and measured volume of ORS or water should be provided for free access instead, with the entire volume of consumed liquid measured and recorded in the charts.

- Vital signs: body temperature, heart rate, respiratory rate, blood pressure (including orthostatic blood pressure measurement when possible), and urine output.
- Blood collection (5 ml) for Complete Blood Count (CBC), Basic Metabolic Panel (BMP) including serum electrolytes and creatinine at treatment dose #5.
- Stool collections for efficacy analysis starts immediately after participant receives the first dose of IP and continues for the entire duration of the treatment. Stool samples are collected continuously, and weighed at 12-hour intervals. Number of stool passages and stool weight is recorded in CRFs.
- At the end of the treatment the last physical exam is performed as per the schedule of events and stool sample will be sent for *V. cholerae* culture to confirm elimination of the pathogen. During the pre-treatment and treatment periods the data will be recorded into provided CRFs by the PI or his designee.

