4.11. Discontinuation of Trial Intervention and Participant Withdrawal from Trial

Participants may withdraw from a research study for any reason, even without mentioning any reason. The participants will be able to receive standard treatment of the hospital without any penalty. For evaluation and reporting purposes, researchers may ask participants for their reasons for early withdrawal.

An investigator may discontinue trial intervention or withdraw a participant from the study for the following reasons:

- Significant study intervention non-compliance.
- If any adverse event (AE), Serious adverse events (SAE), laboratory abnormality, or other medical condition or situation occurs, continued participation in the study would not be in the best interest of the participant.
- Disease progression which requires discontinuation of the study intervention
- If the participant meets an exclusion criterion (either newly developed or not previously recognized) that precludes further study participation.
- Participant unable to receive study intervention for 3 days.
- Reporting over-dose
- protect a participant from excessive risk or risk with a demonstrated lack of benefits (e.g., a participant experiences serious side-effect without the anticipated therapeutic effects), or
- maintain the integrity of the data (e.g., a participant is not following study procedures or may be deliberately providing false information).

Whenever an investigator terminates a subject's participation in research, the investigator must explain to the participant the reasons for the termination and, as appropriate, other treatment options available to the participant.

The data to be collected at the time of study intervention discontinuation will include the following:

- Physical examination
- Vital signs
- Complete blood count (CBC)
- Blood Basic metabolic panel, including Serum electrolytes and creatinine
- Assessment of vomiting
- Assessment of stool output
- Assessment of dehydration
- Assessment of IV and oral ORS and oral water intake
- Assessment of urine output
- Administration of questionnaires or other instruments helping participants to register symptoms, such as stool charts.
- Assessment of adverse events.

Follow-up calls will be made with patients who completed the protocol with questionnaires focusing on the side effects. Calls will be made once a week during the 28-day follow-up period.

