
 To assess the efficacy of VR-AD-1005 for the treatment of acute diarrhea in cholera patients in combination with standard treatment (rehydration and antibiotics, please see attached SoP for more details) versus standard treatment with placebo. Efficacy is measured as reduction in stool output between the start of treatment until final diarrheal stool before clinical recovery (defined as disappearance of watery stool and two consecutive passages of soft stool) or end of study treatment (treatment duration 72 hours), which is earlier. 	
 Reduction in stool output volume (ml/hour/kg) over a treatment period measured as stool weight and recalculated to stool volume using 1:1 w/v ratio, and plotted as stool output quantity per each 12-hour period for the duration stool collection. 6 points are expected for a 72-hour stool collection. Measurement of stool output will be performed by collecting the stool from a participant into the pre-weighed vessel. The vessel with stool will be weighed on the calibrated scale, the weight of the vessel would be subtracted, and the resulting stool weight recorded into the stool diary form. During weighing of stool, Infection Prevention and control (IPC) standards will be upheld by implementing protection of personnel via using appropriate personal protective equipment. Hand washing before and after stool weighing will be strictly adhered to thereby preventing infection of study personnel. After weighing, stool will be disposed of as biohazardous waste at study sites and the weighing vessel appropriately disinfected before next measurement or discarded, if disposable. 	
 Primary endpoint allows to monitor and characterize the efficacy of VR-AD-1005 for reduction of stool output. Over-secretion of hypotonic fluid occurs predominantly in the small intestine, and fluid is lost with stool. The volume of fluid loss in cholera patients can be life-threatening due to rapid dehydration. Thus, the primary efficacy endpoint is designed to demonstrate potential of VR-AD-1005 treatment to reduce fluid loss with stool.
Secondary		

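### Sections 6.2.1 and 4.5.2 tie the stool total to time on study drug, so a patient stopped before recovery can have an understated total that counts as complete

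*Combined protocol and SAP*

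**What the plan says.** **Where the total follows treatment.** Section 6.2.1 proposes two approaches. For the first, "Approach 1 will be based on the total quantity of stool purged by participant during the intervention administration period", expressed in g/kg, which is also the variable used for the sample size in 5.0. Section 4.5.2 matches it: "Stool collections for efficacy analysis starts immediately after participant receives the first dose of IP and continues for the entire duration of the treatment". Section 4.0 lets treatment run for fewer than three days if the patient recovers.

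**Where the window is 72 hours.** Table 1 in 5.0 ends the measure at clinical recovery "or end of study treatment (treatment duration 72 hours), which is earlier", and expects six 12-hour points. Section 6.0 defines the primary endpoint by 12-hour collections over 72 hours.

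**How drug can end before recovery.** Section 4.11 lists, among the reasons to discontinue drug or withdraw a participant, "Disease progression which requires discontinuation of the study intervention" and "If any adverse event (AE), Serious adverse events (SAE), laboratory abnormality, or other medical condition or situation occurs" where continuing is not in the participant's interest. After an emergency code break, 4.4.6.3 says: "The patient will be withdrawn from the study".

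**What is measured then.** Section 4.11 introduces its list with "The data to be collected at the time of study intervention discontinuation will include the following". Stool output is on that list, but as an assessment at that time. No section describes weighing stool from then until recovery or 72 h.

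**Who is analysed.** Section 6.2.1 allows no subtractions from ITT after randomization. Section 4.11 does not replace treated patients who leave. Section 6.2.2 applies multiple imputation to missing values, or lets cases be dropped if they are under 5% of the sample.

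**The concern.** For a total, lower is better. If the counting period ends with the drug, a patient stopped at 12 h while still purging has a 12-hour total that meets the 6.2.1 definition in full. Nothing is missing by that definition, so the rules in 6.2.2 are not triggered, and the patient enters the ITT mean with an understated value.

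Stopping recovered patients does no such harm, because little stool is lost. The problem is stops before recovery. These may be related to severity (progression) or to treatment (adverse events), so they need not be equal between arms. More early stops on active would create or inflate an apparent benefit, and more on placebo would hide a real one. Stool that was not weighed cannot be recovered at analysis, so this has to be settled in the collection procedures.

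**Working it through.** **Inputs from the plan.** Control mean 280 g/kg, SD 156 g/kg, 33% reduction, two-sided alpha 0.05, 50 or 75 per arm (5.0); average duration of diarrhea 30–35 h (6.3).

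**The plan's own figures.** Difference = 0.33 × 280 = 92.4 g/kg; expected active mean = 280 − 92.4 = 187.6, about 188 g/kg. Noncentrality = 92.4 / (156 × √(2/n)) = 2.96 at n = 50 and 3.63 at n = 75. The two-sided t-test then has power 0.835 and 0.950, against the stated 0.82 and 0.94. The figures reproduce to within two percentage points, and this point does not alter them.

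**One average patient stopped at 12 h (counting ends with drug).**
- Constant rate over 30 h: 280 × 12/30 = 112 g/kg, 60% lost.
- Constant rate over 35 h: 280 × 12/35 = 96 g/kg, 66% lost.
- Rate falling linearly to zero at 33 h: x = 12/33 = 0.364; share passed = 2x − x² = 0.595; 280 × 0.595 = 167 g/kg, 40% lost.

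All three lie below 188. At a constant rate, a stop at 24 h loses less: 20% over 30 h and 31% over 35 h.

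**Effect on the comparison: active-only stops.** The plan gives no stop rates, so these are scenarios. If a share p of one arm stops early at random and each stopper loses a share L, that arm's mean falls by p × 280 × L. Take no drug effect, p = 0.10 on active only, and stops at 12 h:
- linear decline over 33 h, L = 0.405: 0.10 × 280 × 0.405 = 11.3 g/kg;
- constant rate over 33 h, L = 0.636: 0.10 × 280 × 0.636 = 17.8 g/kg.

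Simulated trials with 75 per arm (gamma or lognormal totals, mean 280, SD 156) give a two-sided error of about 0.07 and 0.11 respectively, against a nominal 0.05. At p = 0.02 the shift is 2.3–3.6 g/kg and the error stays near 0.05.

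**Other patterns.**
- *Placebo-only stops.* If 10% of placebo patients stop, all from the higher-purging half and each losing half the total, simulated power at 75 per arm falls from about 0.94–0.95 to 0.82.
- *Balanced stops.* With 10% random stops in both arms and no drug effect, the error stays near 0.05. With the planned effect, the difference shrinks only to 92.4 × (1 − 0.10 × L), about 87–89 g/kg.

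**The case against.** **The window may already be 72 h.** Table 1 and section 6.0 can be read that way. Section 4.3 keeps patients on the ward for the three treatment days and lists stool weighing among the procedures of that stay. The administration period in 6.2.1 could then mean the planned three days. This stands as a possible reading, so the documents show an ambiguity and not a settled rule. It does not remove the point, because 4.5.2 still ties collection to treatment and 4.11 asks only for an assessment at discontinuation.

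**Approach 2 behaves differently.** Per 12-hour period, an early stopper has empty later periods, which could fall under 6.2.2. The Table 1 unit, ml/hour/kg, could even make an early stopper look worse if divided by hours on drug. Both stand, and the plan does not say which approach is primary. A reader might infer that the primary measure as a whole is reversed; the documents do not support that.

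**Stoppers may be excluded instead.** Section 4.4.6.1 assigns to groups the data of those who completed the trial, and 5.0 counts withdrawal among lost data points. These conflict with the no-subtractions rule in 6.2.1, and either way the later stool goes unmeasured.

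**The worst patients would not generally score well.** A reader might infer that the most severe courses are recorded as good outcomes. Under a lognormal with the plan's mean and SD, the top 10% of purgers average about 625 g/kg. Stopped at 12 of 33 h they score 625 × 0.364 = about 227 (constant rate) or 625 × 0.595 = about 372 (linear decline), both above 188. Their totals are understated but still poor.

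**Conclusion.** The point holds in limited form. On the 6.2.1 and 4.5.2 reading, a patient stopped before recovery has a truncated Approach 1 total that counts as complete, and other sections describe a different window. The loss for an average patient stopped at 12 h is about 40–66% of the total, given the assumed output profiles.

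The effect on the treatment comparison is unknown, since it depends on stop rates and their imbalance, which the documents do not give. At 10% random active-only stops it is a false benefit of about 11–18 g/kg and an error of about 0.07–0.11. It can run in either direction and is small if stops are rare or balanced. A reader might infer a demonstrated bias in favour of the drug; nothing in the documents establishes that. This should be fixed because it is cheap to fix, but it does not show the primary comparison to be invalid.

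**What to change.** 1. **One window.** Reconcile 4.5.2, Table 1 in 5.0, 6.0 and 6.2.1 to: stool from first dose to clinical recovery as defined in Table 1, or 72 h, whichever is earlier, regardless of whether study drug continues. Keeping the recovery cut-off avoids a new conflict with Table 1.
2. **Collection.** In 4.5.2 and 4.11, continue weighing stool over that window for every randomized patient who remains on the ward and has not withdrawn consent, including after a code break.
3. **Missing periods.** In 6.2.2, state that periods in the window without collection are missing, and are neither zero nor part of a complete total.
4. **Retention.** Reconcile 4.4.6.1 and the withdrawal statement in 4.4.6.3 with the no-subtractions rule in 6.2.1, so that these patients' data are kept.
5. **Primary approach.** State in 6.2.1 which of the two approaches is primary.

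This changes measurement and analysis only. When drug is stopped, and how the patient is managed after a code break, remain for the sponsor to settle. The cost is protocol wording and a few extra weighings on a ward that already has scales and stool charts.
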